1.0 Objectives

1.1 Study Objectives

The objective of this study is to test the effect of a range of doses of a novel nicotine film on plasma nicotine levels and, via a questionnaire, subjective ratings of the film and side effects. We predict that delivery of nicotine via the film will produce plasma nicotine levels akin to other methods of nicotine replacement therapy (NRT) and that it will be easy to use, safe, and well tolerated. The nicotine film is not part of standard of care and is not available in a non-investigational setting in the United States.

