1.3 Secondary Study Endpoints

The secondary endpoint is subjective ratings of the film and side effects in order to determine whether blood levels are of significant magnitude for the participant to detect drug effects.

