7.2 Study Procedures

Part 1- Screening (Phone)

Participants will be instructed to drink water prior to their visit to help the blood draw process go smoothly. They will also be instructed that they may choose to have a meal from our cafeteria but may also bring snacks if they would like. Participants will also be informed that they can bring personal items such as laptops, books, etc. for use during their visit.

Part 1-Screening (In Person)

Participants will be re-screened for eligibility and informed consent for the appropriate part of the study will be obtained by research staff.

After consent, additional eligibility screening materials will include:

1. A review of medications and medical history
2. NIDA Drug Screener
3. Blood Pressure (systolic must be \leq 140, diastolic must be \leq 90)
4. Urine pregnancy test (if applicable)
5. Exhaled Carbon Monoxide <12 ppm

Part 1 Visit – 4 Hours

Clinical measures and questionnaires will be conducted as outlined in the table below. An IV will be inserted for access for 11 blood draws in Part 1.

Part 1: Time and Events Table						
	Screening	Part 1 Procedures				
Visit Hour	-2	-1	0	1	2	3
Administer Film			X			
Blood Draws (mins)			0-59	60-119	120-179	180-239
Baseline Blood		X				
Hour 0 Blood			Set Minutes: 5, 10, 20, 30, 40, 50 Varied by Participant: 1 minute after film dissolves			
Hour 1 Blood				Minute 60		
Hour 2 Blood					Minute 120	
Hour 3 Blood						Minute 180
Measures						
Screener 2	X					
Concomitant Meds	X					
Medical History	X					
NIDA	X					
CES-D		X				
Oropharyngeal Exam		X				X
Blood Pressure & Heart Rate	X	X	Minute 30	Minute 0, 30	Minute 0, 30	Minute 0, 30
CO Reading	X					X
Pregnancy Test	X					
Anthropometrics		X				
Demographics		X				
Nicotine Dependence		X				
Cigarette Details		X				
Tobacco Use History		X				
Minnesota Withdrawal Scale		X	Minute 15, 35, 55	Minute 20	Minute 20	Minute 20
Questionnaire of Smoking Urges		X	Minute 15, 35, 55	Minute 20	Minute 20	Minute 20
Study Product Side Effects			Minute 15, 35, 55	Minute 20	Minute 20	Minute 20
Study Product Evaluation						X
Likelihood of Use Scale						X
Payment						\$120

Film Administration, Dose and Blood Draws:

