9.2 Statistical methods

Paired sample t-test (or nonparametric Wilcoxon Rank-Sum test) will be used to examine the changes in the outcome measures (plasma nicotine, subjective measures, HR, BP) from the baseline.

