11.6 Frequency of review of cumulative data

All the data from the first part of the study (including the results of the blood nicotine analyses) will be reviewed by the leadership group, including [name], before initiation of the next part. If necessary, the doses planned for the next part or the timing of the blood samples may be adjusted accordingly and a modification of study protocol submitted to the IRB.

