11.7 Statistical tests

Statistical methods will be used to analyze the safety data to determine whether harms are occurring. Paired sample t-test (or nonparametric Wilcoxon Rank-Sum test) will be used to examine the changes in the outcome measures (plasma nicotine, subjective measures, HR, BP) from the baseline.

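### The only planned test is change from baseline: neither active film versus 0 mg nor one dose versus another is compared, and the secondary endpoint is left without a usable analysis

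*Combined protocol and SAP*

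**What the plan says.** The statistical methods fill one sentence in section 9.2. It names a "Paired sample t-test (or nonparametric Wilcoxon Rank-Sum test") that "will be used to examine the changes in the outcome measures (plasma nicotine, subjective measures, HR, BP) from the baseline". Section 11.7 repeats the sentence for safety, introduced by "Statistical methods will be used to analyze the safety data to determine whether harms are occurring". Neither section names arms, doses, a contrast or a model with a group term.

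Other sections set up a comparative design:

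- Section 1.1: "The objective of this study is to test the effect of a range of doses of a novel nicotine film on plasma nicotine levels".
- Section 7.1: both parts are randomised, double-blind and parallel-group.
- Section 7.2: each part has three arms of four. Part 1 gives 0, 2 or 4 mg once. Part 2 gives the sequences 0,0,0,0, 2,2,2,2 or 4,4,0,4.
- Section 1.3: "The secondary endpoint is subjective ratings of the film and side effects in order to determine whether blood levels are of significant magnitude".
- Section 9.1 argues from n=12 and gives no alpha, effect size, SD or numerical power.

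**The concern.** A 0 mg arm is randomised, blinded and sampled in both parts, but no planned analysis uses it as a control. A before-after change within an arm mixes any film effect with the effects of time, abstinence and a long clinic visit. Section 12.0 itself expects withdrawal, possibly more serious on 0 mg film.

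Followed as written, the plan would yield either separate before-after verdicts for each arm or one pooled verdict. It would give no film-minus-0 mg estimate, no dose comparison and no analysis of the secondary endpoint. Section 11.7 would judge harms by the same uncontrolled test.

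The nonparametric option is also misnamed. Rank-sum compares two independent samples; the counterpart of the paired t-test is signed-rank.

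**Working it through.** **No figure to reproduce.** Section 9.1 gives n=12 without inputs. Below I assume two-sided alpha 0.05, normal data and effects in SD units.

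**1. Which outcomes have a pre-film value?** From the two Time and Events tables in section 7.2:

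| Outcome | Before film | After film |
|---|---|---|
| Plasma nicotine, HR, BP | yes, both parts | yes |
| Withdrawal and urge scales | yes, Hour -1, both parts | yes |
| "Study Product Side Effects", Part 1 | none | 6 (Hour 0 at 15, 35, 55 min; minute 20 of Hours 1, 2, 3) |
| "Study Product Side Effects", Part 2 | none | 8 (first at Hour 0, minute 50) |
| "Study Product Evaluation" | none | Part 1 once, Part 2 twice |

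The last three rows are the endpoint defined in 1.3. With no baseline there is no change from baseline to test.

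**2. Pooled or per arm.** A pooled Part 1 analysis estimates (change at 0 mg + change at 2 mg + change at 4 mg)/3, which is the effect of no single dose. Per arm, an exact signed-rank test with n=4 has a smallest two-sided p of 2/2^4 = 0.125, so it can never reach 0.05.

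**3. Drift illustration, for HR, BP, withdrawal and urges only.** Suppose all arms drift by d SD of the change and the film does nothing. The paired t statistic is then noncentral t with n-1 df and noncentrality d√n.

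| d | significant, n=4 | significant, n=12 |
|---|---|---|
| 0.5 | 0.11 | 0.35 |
| 1 | 0.29 | 0.88 |
| 2 | 0.75 | >0.99 |

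At d=1 with three independent arms of 4:

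- At least one active arm significant: 1 - (1 - 0.289)² = 0.49 (simulated 0.50).
- An active arm significant while 0 mg is not: 0.49 × (1 - 0.289) = 0.35 (simulated 0.35).
- A between-arm t-test in the same simulation: 0.05.

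**4. Plasma nicotine.** Without film, and without smoking during the supervised visit, residual nicotine only decays, so any drift is downward. With downward drift of 0.5 or 1 SD and no film effect, a significant rise at n=4 has probability about 0.003 or 0.0002. The error here is understatement of delivery. Its size depends on the baseline level, which the documents do not give; if baseline is near zero it is negligible.

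**5. What a between-arm contrast can show with 4 v 4.**

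- Unadjusted, 6 df: 95% CI half-width = 2.447 × √(1/4 + 1/4) = 1.73 SD. Power is 80% for a difference of 2.38 SD, 66% for 2 SD and 22% for 1 SD.
- Baseline-adjusted, 5 df: with identical baseline means the half-width would be 2.571 × √(1/2) = 1.82 residual SD. Chance baseline imbalance inflates the variance by 1.25 on average, giving a mean half-width of about 2.0 residual SD and 80% power for about 2.7 residual SD.
- Break-even: adjustment narrows the interval when 2.0 × √(1 - r²) < 1.73, that is, when the baseline-outcome correlation r exceeds about 0.5.
- Three unadjusted pairwise contrasts: about a 12% chance of at least one false positive if the film delivers nothing (simulated 0.12).

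**The case against.** **A rise in plasma nicotine after film may be plain without a control.** This is partly right. Decay cannot imitate delivery, and a reader who carried the 0.29 and 35% figures over to plasma nicotine would be wrong. But a visible rise still gives no dose comparison, and the argument does not cover HR, BP or the secondary endpoint.

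**Rank-sum is a two-sample test, so an arm comparison may be intended.** The sentence offers it as the alternative to a paired test on change from baseline and names no groups. It reads as a slip for signed-rank.

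**Section 9.2 says subjective measures, and some of these have a baseline.** That is correct: the stated test can be run on withdrawal and urges. Nor is it a scheduling error that a film is rated only after use. The defect is narrower: the endpoint named in 1.3 has no usable analysis.

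**Part 1 is reviewed in full before Part 2.** Section 11.6 allows that "the doses planned for the next part or the timing of the blood samples may be adjusted accordingly". A reader might infer that the leadership group would have to decide without any dose comparison. The documents do not support that: the group sees all Part 1 data, including blood nicotine, and no dose change is tied to a test. The most that can be said is that no between-arm summary is prespecified for the review.

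**Four per arm is too few for formal contrasts.** Power is indeed low. That argues for estimates with intervals, not for leaving the control arm unused.

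**Conclusion.** The omission stands and must be fixed. It rests on the text alone: sections 9.2 and 11.7 contain every planned test, and none compares arms. The objective of testing a range of doses therefore has no planned comparison, and the secondary endpoint has no usable analysis.

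The drift figures (0.29 per arm; 35% for an active arm alone reaching significance) illustrate the risk for HR, BP, withdrawal and urges. They rest on an assumed common drift of 1 SD and normal changes; the documents give no drift size. For plasma nicotine the before-after change could only understate delivery, assuming no smoking during the visit.

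A reader might also want a power figure for 4 mg versus 2 mg in nicotine units. The documents give no variability, half-life or baseline level from which to derive one, so precision is stated here in SD units only.

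**What to change.** Reword 9.2 and 11.7 to analyse each part separately by between-arm comparison.

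- **Plasma nicotine:** prespecify one summary, for example AUC over the sampling period. In Part 1 report 4 mg minus 0 mg (main contrast), 2 mg minus 0 mg and 4 mg minus 2 mg. In Part 2 report each active sequence minus 0,0,0,0, with one named as main. Give all as estimates with 95% CIs.
- **Side-effect and film ratings:** compare post-film values, active versus 0 mg, with no baseline term.
- **HR, BP, withdrawal and urges:** compare active with 0 mg, using the baseline value.
- **Paired changes:** keep as description only, correct rank-sum to signed-rank, and note the 0.125 floor at n=4.

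This costs wording only, with no added participants, draws or visits. The drawback is the low precision shown in the working: non-significant contrasts must not be read as absence of effect, and baseline adjustment pays only where baseline predicts the outcome well. Naming one main contrast per part answers the roughly 12% chance of a false positive across three.

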10.0 Confidentiality, Privacy and Data Management

10.1 Confidentiality

All study data will be collected and managed using REDCap (Research Electronic Data Capture). REDCap is a secure web application designed to support data capture for research studies, providing user-friendly web-based case report forms. REDCap is HIPAA compliant. Data are stored on a secure server at Hershey Medical Center and data in REDCap are encrypted. Access to the database requires authentication (a unique username and password) and a user matrix will be used to ensure that only appropriate data are accessed based on the individual's role on the project. Every interaction with the data is logged in REDCap creating an audit trail.

10.1.1 Identifiers associated with data and/or specimens

The following personal identifiers will be collected:

- Name
- Address
- Phone numbers
- Email addresses
- Date of birth
- Social security number

10.1.1.1 Use of Codes, Master List

All study data will be collected in REDCap including a participant record number and a study specific code number. The list connecting the participant data to the code numbers will be stored electronically in REDCap and will not be destroyed. The PIs, Study Coordinators, Research assistants and Lab Manager will have access to the list.

10.1.2 Storage of Data and/or Specimens

• Electronic data:

- Your research records will be labeled with a code number and will be kept indefinitely in a secure Research Electronic Data Capture System (REDCap) on a password protected, IT maintained, encrypted computer in [name] locked research office.
- A list that matches your name with your code number will be kept in a password protected electronic file.

• Paper records:

- Your paper records (e.g. consent forms) will be kept in a safe area in [name] locked research office. Paper records may also be scanned and uploaded into participant records in REDCap. Paper will be retained until the end of the study after which it will be destroyed.

• Specimens:

- Specimens will be stored with a code number attached.
- Prior to processing, samples will be placed in a refrigerator by the study nurse, research assistant or study coordinator in the key-card secured lab on the third floor of the Cancer Institute.

- Within 24 hours, samples will be processed by a lab manager and will then be secured in a freezer located in a locked room within the research laboratory on the 3rd floor of the Cancer Institute.

10.1.3 Access to Data and/or Specimens

Study data in REDCap: Primary study personnel including: Primary Investigators, Study Coordinators, Research Assistants, and the Lab Manager will have access to the REDCap data. However, a REDCap user matrix will limit access to data based on the researcher's role in the study.

Specimens: Only the lab manager will have access to the specimens once they have been processed and secured in the locked freezer room.

10.1.4 Transferring Data and/or Specimens

N/A

10.2 Privacy

The research team will only have access to data that a participant provided during data collection contacts. HIPPA guidelines will be followed for all participants and they will be provided with the institution's written Privacy Notice at their screening visit. Participants will be informed that they can refuse to answer any questions that make them feel uncomfortable. The majority of personal data that the participants provide will be entered directly into REDCap by the participant. All study visits, data collection and procedures will be completed in private consult rooms at the Penn State Hershey CRC.

11.2 Data that are reviewed

Data that will be reviewed include:

- Accrual and retention
- Adverse events and serious adverse events
- Protocol deviations/violations
- Changes in subjective effects (particularly dizziness and nausea, the most common nicotine effects)
- Changes in heart rate and blood pressure
- Oropharyngeal changes

11.3 Method of collection of safety information

All data, including safety data, will be coded directly into REDCap electronic case report forms during study visits.

11.4 Frequency of data collection

Safety data will be collected intermittently at each study visit.

11.5 Individual's reviewing the data

The study coordinator will be responsible for the daily oversight of subject safety and will provide updates to the Principal Investigators to review participants' progress and their experiences with the study, including any adverse events.

In the event of adverse event(s) during the conduct of the study, we have a mechanism in place to ensure that the event(s) will be assessed by the Principal Investigators and the study physician and reported to the PSU IRB and NIH in a timely manner. All adverse events (AEs) occurring during the course of the study must be collected, documented, and reported to the Principal Investigators and [name], Professor of Medicine and Chief of Division of Internal Medicine at Penn State Hershey,. All AEs will be assessed by the Principal Investigator to determine if they meet criteria for a serious adverse event (SAE). Serious adverse events, as defined by the FDA, will be systematically evaluated at each clinic visit. Any SAE, whether or not related to study participation, will be reported to the IRB, and NIDA. The initial SAE report will be followed by submission of a completed SAE report. Outcome of SAEs will be periodically reported to NIDA. A summary of the SAEs that occurred during the previous year will be included in the annual progress report to NIDA. Each week a study investigator will review the AE Forms from the previous week for events that were reported as new or continuing. The study investigators will follow all AEs to the point of a satisfactory resolution. A study participant may have their participation discontinued if the PI determines it is the best decision in order to protect the safety of a participant.

Where any participant had a serious adverse event (systolic BP>160, vomiting or any other symptoms requiring their participation in the study to be interrupted/terminated), [name] will immediately review the case and make a recommendation both on management of that individual case but also continuation of the study at the planned doses.

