7.3 Duration of Participation

Duration of participation is dependent on which part of the study the participant is enrolled in. The study visit for Part 1 will last approximately four hours. The study visit for Part 2 will last approximately twelve hours.

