12.0 Risks

Potential risks for subjects are minimal. The nicotine films which will be administered to subjects have been previously tested in humans and we do not expect them to provide higher nicotine levels than subjects routinely receive from their smoking. Subjects will have a review of their medical history prior to entry into the study. Subjects will be under supervision throughout their participation in the study and adverse symptoms will be recorded and monitored by the Project Leaders. The major risks associated with the study are related to the use of nicotine (which is similar to the nicotine received from smoking) and nicotine withdrawal.

Additional potential risks include:

- **Nicotine withdrawal symptoms:** It is possible for subjects to experience short-term nicotine withdrawal symptoms (e.g. irritability, restlessness, difficulty concentrating, anxiety). Those receiving placebo films may experience more serious nicotine withdrawal symptoms.
- **Risk to fetus and breast fed infants:** Nicotine is known to be harmful to the developing human fetus, either from cigarettes or at the dose being used in this study. For this reason women must not be pregnant or nursing in order to participate in the study.
- **Risks of IV catheter for blood draw:** The discomfort associated with the IV insertion by venipuncture (by needle then catheter into a vein) for removing blood is a slight pinch or pin prick when the sterile needle enters the skin. The risks include mild discomfort and/or a black and blue mark at the site of puncture. Less common risks include a small blood clot, infection or bleeding at the puncture site, and on rare occasions fainting during the procedure.
- **Loss of confidentiality:** There is a risk of loss of confidentiality if information is obtained by someone other than the investigators. Precautions will be taken to prevent this including direct coding of data in REDCap.
- **Randomization:** Participants will be assigned to a treatment program by chance.
- **Discomfort from questionnaires:** It is possible that some of the questions in the questionnaires may make participants uncomfortable. They will be instructed that they are free to skip any questions that make them uncomfortable.

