- **Nicotine film side effects:** Excess nicotine can cause mild symptoms such as nausea, dizziness, diarrhea and rapid heartbeat. Occasionally these symptoms are more severe (e.g. vomiting) such as when an individual receives more nicotine than they are accustomed to. This, however, is unlikely to occur with the doses used in this study. Additional side effects of the film may include hiccups.

- **Possible effects on the oral cavity.** In order to assess local toxicity of the study product, the CRC nurse assisting with the clinic visit will perform an oropharyngeal exam at the beginning of the visit prior to the participant receiving the study product as well as at the end of the visit after study product use is complete. Any changes will be assessed and documented. During the visit, after each film administration, participants will be asked to report side effects including any mouth discomfort or irritation via a questionnaire. If indicated, participant would discontinue study product use. Lesions of the oral mucosa are not anticipated as daily dissolution of several 2 mg sublingual nicotine tables (range 1-12/day over a 6 month period) led to only mild and transient effects on the oral mucosa[24]
- **Incidental Finding:** None of the tests carried out in this study are intended to provide diagnoses for clinical purposes, but participants will be alerted to findings that should be discussed with a healthcare provider (such as high blood pressure)

The participant may be removed from the research study without his or her permission because the participant does not follow the instructions for the study, has an adverse reaction to the study product (irregular heartbeat, palpitations, tachycardia (resting heart rate persistently greater than 100 beats per minute), has symptoms of nicotine overdose such as nausea, vomiting, dizziness, weakness, or rapid heartbeat, or has symptoms of an allergic reaction.

Participants are instructed to please call the Principal Investigator, [name] [name]., at [contact] during business hours or [contact] after business hours if they:

- Experience any symptoms after the study is completed that they believe may be related to participation in the study
- Have questions, complaints, or concerns about the research

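### No safety contact is scheduled after discharge, so an event that begins after the single visit is recorded only if the participant calls or happens to be re-screened for Part 2

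*Combined protocol and SAP*

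**What the plan says.** Section 11.4 sets the timing: "Safety data will be collected intermittently at each study visit". Section 11.3 sets the recording: "All data, including safety data, will be coded directly into REDCap electronic case report forms during study visits". Section 11.5 places the evaluation of serious events at clinic visits: "Serious adverse events, as defined by the FDA, will be systematically evaluated at each clinic visit".

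Section 7.3 gives one visit per part: "The study visit for Part 1 will last approximately four hours", and about twelve hours for Part 2. Both Time and Events tables in section 7.2 stop with that visit. Section 3.3.2, on follow-up of withdrawn participants, reads N/A.

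Section 12.0 lists catheter risks: "Less common risks include a small blood clot, infection or bleeding at the puncture site". It puts the last oropharyngeal exam at the end of the visit. It also tells participants to telephone if they "Experience any symptoms after the study is completed that they believe may be related to participation in the study", or if they have questions, complaints or concerns.

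Section 11.5 requires all adverse events in the course of the study to be collected, weekly review of adverse event forms for new or continuing events, and follow-up to satisfactory resolution. It adds: "Any SAE, whether or not related to study participation, will be reported to the IRB, and NIDA". Before Part 2 opens, section 11.6 says: "All the data from the first part of the study (including the results of the blood nicotine analyses) will be reviewed".

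**The concern.** Evaluation at each clinic visit works as surveillance when there is a next visit. Here, someone who joins only one part has none. Nobody on the study team is scheduled to ask that person anything after discharge, and the main prompt to call depends on the participant's own view of cause. A serious event that the participant thinks unrelated is the kind least likely to be volunteered.

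Two things are at stake. The first is participant safety: a complication at the catheter site could go unheard. The second is what an empty record means. Section 1.1 predicts that the film will be safe and well tolerated. If no delayed events are recorded, the reader cannot tell whether none occurred or nobody asked.

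**Working it through.** The plan gives no figure on this point, so there is none to reproduce. The check reads the observation window from the schedule and then illustrates what passive reporting could lose.

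**Window after the last film** (section 7.2 tables, section 7.3)

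- Part 1: film at Hour 0; the table runs to about minute 240. Window = 240 − 0 = 240 min, about 4 h. Last side-effect questionnaire at Hour 3, minute 20: 3 × 60 + 20 = 200 min after the film.
- Part 2: last film at Hour 9 (540 min) of a 12-hour visit (720 min). Window = 720 − 540 = 180 min, about 3 h. The last side-effect questionnaire is at minute 50 of Hour 10 or Hour 11, because the columns are not clearly aligned in the text available: 650 − 540 = 110 min or 710 − 540 = 170 min.
- IV site: the last draw is at minute 180 in Part 1 and at Hour 11 (660 min) in Part 2. If the catheter stays in until then, which is an inference, the time left to observe the site is 240 − 180 = 60 min or 720 − 660 = 60 min.

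**Routes into the record after discharge**

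- Scheduled contact: none in either table.
- Participant's call (section 12.0): available, but started by the participant.
- Part 2 screening (section 7.2): medical history and medications are reviewed again, but only for people who choose both parts, and only after the Part 1 review has closed.
- Weekly form review (section 11.5): works on forms already completed and creates no new contact.

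**Illustration.** Let p be the true rate of a post-discharge event, c the share of such events that reach the team, and n the number of dosed visits. Then P(at least one recorded) = 1 − (1 − pc)^n. Both p and c are assumptions. From section 16.0, n is 12 per part and 12 + 12 = 24 in all; the formula treats visits as independent.

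| n | p | c = 1 (everyone asked, all captured) | c = 0.5 | c = 0.2 |
|---|---|---|---|---|
| 12 | 2% | 22% | 11% | 5% |
| 12 | 5% | 46% | 26% | 11% |
| 12 | 10% | 72% | 46% | 22% |
| 24 | 5% | 71% | 46% | 21% |
| 24 | 10% | 92% | 71% | 38% |

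For rare events even full capture finds little: with n = 24, p = 1% gives 1 − 0.99^24 = 21%, and p = 0.5% gives 1 − 0.995^24 = 11%.

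**The case against.** The strongest reply is that visit-based collection fits a study this short. Nausea, dizziness, heart rate and blood pressure are the effects the plan expects, and they are measured repeatedly in the visit. That stands.

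A reader might also infer several stronger points, which the documents do not support:

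- *That section 11.5 contradicts itself.* The rule on reporting serious events regardless of relatedness, and the rule on following events to resolution, both govern events the team knows of. Section 11.5 starts the IRB reporting clock when information is received, and section 21.2 speaks of events observed or reported to the team. Staff can follow a known event after discharge without a scheduled call.
- *That calls are restricted to symptoms the participant thinks related.* Section 12.0 also invites questions, complaints and concerns, gives an after-hours contact, and asks only that a link be possible. A sore arm or mouth is easily connected with the catheter or film.
- *That delayed mucosal injury is expected.* No passage says film effects can first appear after 3 to 4 hours. Section 12.0 gives a reason not to expect lesions: only mild and transient effects with repeated daily sublingual tablets over six months.
- *That the Part 1 review is undermined.* That review can adjust doses or sampling times. Catheter complications bear little on either.

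It can also be argued that participation is the visit (section 7.3) and that section 12.0 treats later time as after the study. This is a plausible reading, but no passage states when collection ends.

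**Conclusion.** The concern holds in a limited form. There is no active ascertainment of events that start after discharge, about 4 h (Part 1) or 3 h (Part 2) after the last film, for any of the 24 planned completed visits, which may involve as few as 12 or as many as 24 people. The end of the adverse event collection period is also undefined.

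The window and the absence of a scheduled contact come directly from the documents. How much would be lost does not: the rates and capture shares in the table are assumptions, and the documents describe the IV-site clot, infection and bleeding only as less common. The case for a change rests on its low cost and on participant safety. It does not rest on any demonstrated error in the endpoints, which are plasma nicotine and in-visit subjective ratings and side effects.

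**What to change.** - Add one scheduled coordinator phone contact to both Time and Events tables after every dosed visit. Include participants withdrawn after dosing, and replace the N/A in section 3.3.2 accordingly. The sponsor should choose and state the interval; the documents give no basis for a particular one.
- Use the existing side-effect form, with added questions about the mouth, the IV site and any medical care received, whatever the suspected cause.
- State that adverse event collection ends at that contact. Amend sections 11.3, 11.4 and 11.5 so that safety data are collected, entered and evaluated at the visit and at the follow-up contact.
- Include the Part 1 contacts in the data reviewed under section 11.6.

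The cost is about 24 short calls by existing staff (plus any for participants withdrawn after dosing), a line in each consent form, a REDCap form and a short delay before the Part 1 review closes. No dose, film schedule or clinical rule changes.
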